5.0 Study Design

Using a Phase II blinded, randomized placebo-controlled trial, with optional open label extension period, we will evaluate armodafinil's ability to reduce patient-reported fatigue in patients with treated head and neck cancer. This type of trial design is especially important in trials where symptom reduction is the outcome and where knowledge of the treatment arm might bias assessment by the staff or patient. We will purchase commercial grade drug and matching placebo to be dispensed by the investigational pharmacy.

Design: Phase II blinded, randomized placebo-controlled trial, with optional open label extension period

Symptom Intervention Agent: Armodafinil

Study Period: 8-12 weeks depending on participation in the optional open label component : intervention agent daily for 4 weeks (Part I), with continued assessment follow-up period of 4 weeks (Part II). At the end of the 4-week agent intervention, the patient will be given the option to receive open label armodafinil during the 4 weeks follow-up period. If the patient agrees to this option, the follow-up period for these patients will be extended for another 4 weeks.

Primary Symptom Outcome Variable: 4-week (+/- 7 days) area under the curve (AUC) for patient-reported fatigue at its worst (item from the Brief Fatigue Inventory).

Secondary outcomes assessed will include: (1) the 5 most-severe MDASI-HN symptoms at 2-month follow up based on previously collected MDASI-HN data (2) overall MDASI-HN symptom severity, (3) overall MDASI-HN interference, (4) patient-reported alertness (via Epworth Sleepiness Scale), and (5) work productivity and activity impairment questionnaire.

Forty patients will be randomized to either armodafinil or placebo, twenty in each arm. AUC values for patients who drop out of the study after providing 2 weeks of AUC data will be included by carrying their last symptom data forward for the remaining study period under the intent-to-treat rule. The carry-forward method of handling drop-outs will be revisited upon completion of the study to determine if adjustments to these values can be made using longitudinal regression models estimated from patients who completed the entire study.

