13.0 Statistical Analysis Plan

13.1 Sample Size and Randomization

Forty patients will be randomized equally to the 2 treatment arms - armodafinil and placebo. With 20 patients per treatment arm, we will be able to detect a 0.70 SD effect size on the BFI AUC between the 2 treatments with 70% power and one-sided 5% significance test. A 0.70 effect size for the BFI is about **1.7 points (change in terms of AUC)** on a 0 to 10 scale. Because this is a small Phase II study with the intent of providing effect size estimates to inform a large clinical trial in the future, we chose a modest statistical power.

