13.2 Analysis Plan

We will test armodafinil in its ability to reduce values of patient- reported fatigue scores. Our emphasis is to test the efficacy of armodafinil as a potential agent in reducing patient-reported symptoms in patients with HNC after planned cancer therapy. The proposed phase II clinical trial for screening this potentially effective symptom-intervention agent will provide moderate power in detecting modest intervention effect. If the treatment has a more pronounced effect, it will be detected with higher power.

This study will allow us to obtain estimates of treatment effect and the variability of these estimates. Estimates of treatment effect will be obtained using standard linear regression techniques in which AUC values ($hn(i)$) are regressed on indicator variables that represent treatment received. Estimates of treatment effect and between-subject variability will then be used to design a more comprehensive study in future clinical trials.

In addition to the formal evaluation of treatment effects on the primary outcome, we will also examine the prognostic effects of disease stage, type of cancer treatment, ECOG status, age and gender in predicting the outcome variable. We will compare the percentages of patients who were satisfied with the study drug against those who were taking the placebo. We will include an indicator variable in our model to determine whether patients who had a full dose of armodafinil differ from those who had a run-in period. Standard exploratory data analysis techniques and descriptive statistics will be used.

Assuming that patients accrue at the rate of 4 per month, we anticipate that this pilot study will require approximately 14 months to complete.

Intent to treat

We will need at least 2 weeks of BFI data for the patient to calculate AUC. Any patient who drops out prior to this will be replaced.

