13.21 Primary Outcome Variable

The primary outcome variable will be the combined AUC for the “fatigue at its worst” item of the BFI. The value of this variable for patient i is denoted $bfi(i)$ and is comprised of the BFI scores collected during the 8 weeks of the study period.

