13.22 Secondary Outcome

We will use linear mixed models determine whether the placebo and the armodafinil groups differ on our secondary outcomes: the 5 most-severe symptoms, symptom interference, work productivity, and sleepiness.

We are also interested in exploring predictors of survival. Univariate Cox proportional hazards models will be used to screen for potential predictors (symptoms, demographic and clinical variables) of overall survival. Standard model fitting diagnostics will be performed. Finally, Kaplan-Meier survival curves will be plotted.

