13.23 Non-Compliance with Study Agent

Patients who do not comply with study agent dosing requirements will remain in the study under the intent-to-treat rule.

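### Section 13.2 codes the primary AUC regression by treatment received, which conflicts with an intent-to-treat rule that the plan invokes but does not define

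*Combined protocol and SAP*

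**What the plan says.** Section 13.2 gives the only specification of the treatment-effect regression: AUC values "are regressed on indicator variables that represent treatment received".

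Other parts of the plan point to the randomised arms:

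- 13.1: "Forty patients will be randomized equally to the 2 treatment arms", and the power statement compares those two arms.
- 13.22 asks "whether the placebo and the armodafinil groups differ on our secondary outcomes".
- 5.0 includes patients who drop out after 2 weeks "by carrying their last symptom data forward for the remaining study period under the intent-to-treat rule".
- 13.23: "Patients who do not comply with study agent dosing requirements will remain in the study under the intent-to-treat rule".
- 13.2 has its own subheading on intent to treat. The text under it requires 2 weeks of BFI data and replaces anyone who leaves sooner.

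Two further features bear on how far receipt and assignment can part. The primary outcome in 5.0 is a "4-week (+/- 7 days) area under the curve (AUC) for patient-reported fatigue at its worst", whereas in 13.21 it "is comprised of the BFI scores collected during the 8 weeks of the study period". After week 4, "the patient will be given the option to receive open label armodafinil during the 4 weeks follow-up period".

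Section 13.2 also adds an indicator separating patients who had a full dose of armodafinil from those who had a run-in. Section 6.0 describes a single stepped schedule for everyone.

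**The concern.** Randomisation makes the arms comparable as assigned, not as received. Not taking the drug, or choosing open-label drug later, may be related to fatigue, which is the outcome. If such patients are moved between groups according to what they took, the estimate can be biased in either direction even when the drug does nothing.

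The intent-to-treat statements do not settle the coding. Section 5.0 deals with carrying values forward, 13.23 with keeping non-compliers in the study, and the text under the 13.2 subheading with minimum data and replacement. A patient kept in the study can still be coded by receipt. An analyst following the regression sentence and one following the intent-to-treat rule in its usual sense could therefore fit different primary models, and the choice could be made after the data are seen.

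Sections 13.1 and 13.2 say that the trial's purpose is to supply effect-size and variability estimates for a larger trial, so a bias here would carry into that design.

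**Working it through.** **1. The plan's own figure.** Inputs from 13.1: 20 per arm, effect 0.70 SD, one-sided 5%. Noncentral t with 38 degrees of freedom and noncentrality 0.70 × √(20/2) = 2.21 gives power 0.702. The normal approximation gives 0.715. The stated 70% reproduces. It is the power of the comparison between the two randomised arms.

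**2. When the codings agree.** If every patient receives the assigned treatment, the two regressions are identical. In weeks 1 to 4 treatment is blinded and dispensed from a pharmacy-held list (9.0), so they differ only for patients who take none of their assigned drug or through a dispensing error.

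**3. Four-week AUC, illustration.** The documents give no rate of non-receipt and no selection effect, so both are assumed. Suppose there is no drug effect, and *k* of the 20 armodafinil patients take no drug, supply enough BFI data to be analysed and are coded as placebo. Suppose they differ by δ SD from the other armodafinil patients, with the whole arm's mean at 0.

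- Mean of those recoded: δ(20 − k)/20. Mean of the remaining armodafinil patients: −δk/20.
- Mean of the enlarged placebo group: [k/(20 + k)] × δ(20 − k)/20.
- Bias = (kδ/20) × [(20 − k)/(20 + k) + 1] = 2kδ/(20 + k).

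The rejection rates come from 200,000 simulated trials per cell, using the pooled one-sided 5% t-test for lower fatigue on armodafinil:

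| k | δ | Bias (SD) | Rejection if recoded patients are more fatigued | Rejection if less fatigued |
|---|---|---|---|---|
| 1 | 0.2 | 0.019 | 0.056 | 0.044 |
| 2 | 0.2 | 0.036 | 0.063 | 0.039 |
| 4 | 0.2 | 0.067 | 0.075 | 0.033 |
| 1 | 0.5 | 0.048 | 0.067 | 0.036 |
| 2 | 0.5 | 0.091 | 0.085 | 0.026 |
| 4 | 0.5 | 0.167 | 0.126 | 0.015 |

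With δ = 0 the rate stays at 0.049 to 0.051. Coded by randomised arm, the bias is 0 and rejection is about 5%.

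Section 13.1 equates 0.70 SD with 1.7 points, which implies an SD of 1.7/0.70 = 2.43 points. The bias range is then 0.019 × 2.43 = 0.05 to 0.167 × 2.43 = 0.41 points.

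**4. Eight-week AUC, conditional.** This applies only if 13.21 prevails over 5.0. Suppose *m* of 20 placebo patients take open-label drug, are coded as armodafinil and differ by δ from the other placebo patients. By symmetry the bias is 2mδ/(20 + m). For m = 2 and δ = 0.2 it is 0.8/22 = 0.04 SD; for m = 10 and δ = 0.5 it is 10/30 = 0.33 SD. In the second case rejection is about 0.23 if those who opt in are less fatigued and 0.005 if more fatigued. If they form a third group instead, the bias in armodafinil versus placebo-only is mδ/20, which for m = 10 and δ = 0.5 is 0.25 SD. The opt-in rate, δ and the coding of mixed exposure are all assumed.

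**The case against.** The strongest reply is that the plan does commit to intent to treat, in three places, and that 13.23 applies it to dosing non-compliance, the main way receipt could differ from assignment in the blinded period. On the usual meaning of the term, those patients are analysed as assigned. Sections 13.1 and 13.22 also compare arms or groups, so the regression sentence may simply be loosely worded. Much of this stands. A reader might infer from 13.2 that the plan lacks any intent-to-treat commitment or intends an as-treated primary analysis. The documents do not support that. They contain two statements that conflict, and nothing that ranks them. The usual meaning cannot simply be assumed either, because the text under the plan's own subheading replaces early drop-outs.

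It is also fair to say that receipt and assignment should nearly always coincide over 4 blinded weeks. A reader might take the instruction in 5.0 to stop drug at the first sign of rash as a route to recoding. It is not a natural one: a patient who stops for rash on armodafinil has already received it, so receipt and assignment still agree.

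The larger 8-week figures need the longer AUC window, substantial opt-in, and patients with 4 weeks of blinded placebo coded as armodafinil. The plan does not state that coding. These figures show what could happen and should not be read as a measured defect.

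On the run-in indicator, a reader might conclude that it can never be estimated. That goes too far. The term is undefined, and it could mean patients who stopped during the stepped first week.

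**Conclusion.** The concern holds as a conflict of wording about the primary model: coding by receipt in 13.2 against an intent-to-treat rule in 5.0, 13.2 and 13.23 that is never defined as analysis by assigned arm. It is worth correcting before analysis, with medium confidence about its practical effect.

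Under the 4-week AUC the likely effect is small. The illustrated bias of 0.02 to 0.17 SD is set against a design effect of 0.70 SD, can go either way, and vanishes if receipt is unrelated to fatigue or everyone receives the assigned treatment. Under the 8-week AUC it could be larger, but how much depends on opt-in, selection and coding that the documents do not give, and on the separate conflict over the window.

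The run-in indicator is a secondary inconsistency between 13.2 and 6.0.

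**What to change.** In 13.2, replace *treatment received* with *the arm to which the patient was randomised*. State there that the intent-to-treat analysis is by assigned arm, and that any analysis by treatment received is supplementary.

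Reconcile 6.0 and 13.2 on whether more than one starting schedule exists. Then either delete the full-dose versus run-in indicator, or define it, label it exploratory and keep it out of the primary model.

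The cost is wording only. Sample size, data collection and power (0.702 for the randomised comparison) are unchanged.

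Three related matters need their own resolution, because recoding does not settle them: the 4-week versus 8-week AUC, dilution of an 8-week contrast by open-label drug, and the replacement of patients who leave before 2 weeks of BFI data.

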A list of adverse events (AEs) known to be associated with primary treatment is listed in section 4.0 of the protocol. Study staff will monitor for AEs via telephone contact with the subjects using the Phone Contact Form according to the Assessment Schedule. In addition, study participants will be able to contact study personnel via a telephone hotline, and study participants can be seen by study personnel at MD Anderson if there are any concerns or questions regarding potential side effects. If seen in person by study personnel, clinical monitoring form will be completed. Also, if study subjects are coming to MD Anderson for

routine clinical follow up (visits unrelated to this study), they will be seen by study staff as frequently as weekly during the study period, and the clinical monitoring form will be completed every time.

Patients will be advised to discontinue drug at first sign of body rash during this study and to immediately notify study personnel, who will in turn notify the PI for appropriate medical management.

All grade 3 and 4 toxicities reported by patients in this trial will be evaluated by the principal investigator in consultation with the treating physician, or by another attending physician if the PI is not available, to determine whether the toxicities were possibly caused by the study medication (rather than being effects from previous cancer therapy). The investigators will discriminate between expected dermatitis related to radiation therapy or chemotherapy versus armodafinil hypersensitivity. If 1 or more armodafinil-related grade 3 or 4 toxicities is observed in the patients assigned to armodafinil, the study will be terminated.

The interaction screening will be the responsibility of the research staff. Study exclusion criteria of known drug interactions and drugs that would require additional monitoring if given in conjunction with armodafinil will also be in place for patient safety. The research staff will review any current or new patient medications prior to initiating treatment, and will document all medications patients have used or will use during the trial. During the trial, the research staff will capture any potential drug interactions that could cause an AE on the Adverse Event forms. Medication sheets will be provided to both patients and treating physicians to inform them of the possibility that the patients may be receiving armodafinil (see Appendix EEE and EE).

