6.0 Administration of Pharmacologic Agent

Armodafinil or placebo will begin after enrollment and will continue daily for a total of 4 weeks.

Patients will pick up the assigned study medication at one of the outpatient pharmacy stations in MD Anderson. At pickup, patients will receive instruction on how to take study medications (Appendix EEE). If the patient is unable to pick up the study medication, the investigational pharmacy will mail the study medication to the patient home, overnight.

The participants will take study medication enterally, once daily, in the morning, starting after study entry and continuing for 28 days (4 weeks). The dosing schedule for the symptom intervention agent is described in the table below.

Study medication use will be reviewed at the end of week 4 by study staff. Patients will be asked to bring their study medication to the clinic if they are coming in for a routine visit, at which time study staff will perform a medication count. If the patient is not coming to the clinic at study completion, the medication review will be completed by telephone. Results of the count will be recorded on the Study Medication Accountability form (Appendix K).

During the end of week 4 assessment, the study staff will also offer the participant the option to receive open label armodafinil, at the same dosing schedule described in the table below. If the patient agrees to the optional open label extension, they will either pick-up armodafinil during their routinely scheduled follow-up visit or the pharmacy will mail it to them. A 5-day window will be allowed between the end of Part I and the start of the optional open label extension.

Symptom Intervention Agent	Dosage Forms	Total daily dose: starting day 1 of week 1
Armodafinil or matching placebo	50mg and 100mg capsules or tablets	50 mg the first 3 days, 100 mg the next 4 days, and 150 mg for the remaining treatment period.*

*capsules or tablets, one every morning, may be given without regard to meals. This dosing schedule is to be followed during the 4-week symptom intervention and the optional open label extension.

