7.15 Laboratory Data Form No study-specific labs are planned; however, any blood-analysis values obtained for clinical reasons will be captured on the Laboratory Data Form, including C-reactive protein (CRP), serum chemistry (albumin, calcium, phosphorous, glucose, BUN, creatinine, total bilirubin, and total protein), electrolytes (sodium, potassium, chloride, carbon dioxide, magnesium), and complete blood count (CBC). These values will be recorded if they are available in the patient medical record from a blood draw performed for clinical purposes within previous 2 weeks. Note: Liver function tests are required at baseline. If they were not performed within the past 2 weeks prior to starting treatment with the symptom drug/placebo, they will be drawn for eligibility purposes. (Appendix W).

7.16 Treatment Summary Form The Treatment Summary Form contains data about previous radiation therapy and cancer treatment (Appendix O).

7.17 Final Study Status Form The Final Study Status Form contains data about patient disposition at the end of the study (i.e., completed study, withdrew, vital status, tumor status) (Appendix Y).

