12.11 Alkaline phosphatase (ALP) is 2 times the upper limit of normal

12.12 Aspartate aminotransferase (AST) or alanine aminotransferase (ALT) is 2 times the upper limit of normal

- 12.13 Total bilirubin >1.5 x ULN
- 12.14 Signs and symptoms of severe rash (CTC version 4 \geq grade 3) or hypersensitivity
- 12.15 Pregnancy during the study period
- 12.16 INR > 1.5. Treating physician notified so that medical management occurs.
- 12.17 Development of psychosis.
- 12.18 Development of symptomatic tachycardia or palpitations or uncontrolled hypertension.

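### The rule headed Intent to treat drops from the primary comparison, and replaces, patients who leave before 2 weeks of BFI data; the set is modified intent to treat

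*Combined protocol and SAP*

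**What the plan says.** Section 13.2, under the heading Intent to treat, requires "at least 2 weeks of BFI data for the patient to calculate AUC. Any patient who drops out prior to this will be replaced". The primary analysis in the same section is a linear regression of AUC values on indicators of the treatment received.

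Section 5.0 draws the same line from the other side: "AUC values for patients who drop out of the study after providing 2 weeks of AUC data will be included", with the last value carried forward and the intent-to-treat label attached. It adds that the carry-forward method will be revisited at the end using longitudinal regression.

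Section 13.23 says that patients who do not comply with dosing "will remain in the study under the intent-to-treat rule". Section 6.0 fixes the order of events: "Armodafinil or placebo will begin after enrollment and will continue daily for a total of 4 weeks". Section 13.1 gives the purpose: "the intent of providing effect size estimates to inform a large clinical trial in the future".

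**The concern.** Intent to treat means that every randomised patient is analysed in the assigned arm. Here membership of the primary set depends on staying long enough to give 2 weeks of scores. Treatment has already begun by then, so staying may depend on the treatment and on how tired the patient is. If early losses differ between arms and relate to fatigue, the two groups compared are no longer the two groups randomised. Refilling to 20 per arm restores the count, not the comparison.

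The main product of this trial is an effect-size estimate for planning a larger one. As written, that estimate describes patients who stayed at least 2 weeks but would be read as an intent-to-treat estimate. The Final Study Status Form (section 7.17) records withdrawals, so the data for a by-arm account exist. The plan does not commit to that account, or to a primary or sensitivity analysis that includes these patients.

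**Working it through.** **Are early dropouts excluded?** No sentence says so outright; it follows from four places read together. Section 13.2 gives no AUC below 2 weeks of data and replaces the patient. The primary model needs an AUC. Section 5.0 includes only dropouts after 2 weeks of data. Section 13.23 concerns dosing compliance and supplies no outcome for a patient who has left. No other reading fits all four.

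**The plan's own figure.** Section 13.1 states 70% power for 0.70 SD, 20 per arm, one-sided 5%. The noncentrality is 0.70 × √(20×20/40) = 2.21 on 38 df, which gives 70.2%. The figure reproduces, for 20 analysable patients per arm.

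**Scale.** SD = 1.7/0.70 = 2.43 points (derived from section 13.1). Standard error of the difference = 2.43 × √(2/20) = 0.77 points.

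**Assumed scenarios.** There is no drug effect. In an arm with k early losses, 20 + k are randomised, and the k highest on a latent score correlated c with fatigue are excluded and replaced. If those k are g points worse than those who stay, the analysed mean shifts by about g × k/(20 + k). Simulated g is 1.0 to 1.2 points for c = 0.25 (moderate) and 2.1 to 2.4 for c = 0.5 (strong). For example, one loss with a strong link gives 2.4 × 1/21 = 0.11, and four give 2.1 × 4/24 = 0.35. Type I error is approximately 1 − Φ(1.645 − shift/0.77); four losses with a strong link give 1 − Φ(1.645 − 0.35/0.77) = 11.7%, against 12.1% simulated with the t-test.

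| Early losses, armodafinil vs placebo | Moderate link: shift in points, type I error | Strong link: shift in points, type I error |
|---|---|---|
| 1 vs 0 | 0.06, 5.9% | 0.11, 6.9% |
| 2 vs 0 | 0.10, 6.6% | 0.20, 8.6% |
| 4 vs 0 | 0.18, 8.0% | 0.35, 12.1% |
| 0 vs 4 | 0.18 the other way, 3.1% | 0.34 the other way, 2.0% |
| 2 vs 2 | about 0, 4.9% | about 0, 5.4% |

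With no link to fatigue the error is 4.9 to 5.2% throughout. Excluding the same patients without replacing them (strong link) gives 6.8%, 8.8%, 12.9% and 1.8% for the first four rows. The exclusion does the damage, not the substitute.

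**What using all scores would recover.** This second model assumes weekly BFI over a 4-week window, 20 randomised per arm, and dropouts who give baseline and week 1 only. A likelihood analysis of all available scores is compared with exclusion.
- Dropout tied to scores already given: error falls from 8.2% to 4.9–5.0% (2 vs 0) and from 10.9–11.7% to 4.8–4.9% (4 vs 0).
- Dropout tied to later, unobserved fatigue: it falls only from 8.5–8.8% to 6.1–6.7%, and from 12.3–12.7% to 6.9–8.3%.
- Baseline only available: 7.0–7.9% and 8.6–10.3% remain.

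**Cost in power** if early dropouts add almost nothing and nobody extra is randomised: 18 vs 20 has noncentrality 0.70 × √(360/38) = 2.15, power 68.0%; 18 vs 18 has 0.70 × √9 = 2.10, power 66.0%.

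**The case against.** The strongest reply is about weight. The rule is stated openly in a 40-patient pilot, and the assumed shifts are small beside the noise: the largest is 0.35/0.77, under half a standard error, and the smallest is 0.06/0.77, about a twelfth. Nothing in the documents gives a dropout rate, a difference between arms or a link to fatigue. Four early losses against none would be 4 of 24, or 17%, of one arm within 2 weeks. All of that stands, and it keeps the point from being fatal. It does not make the label correct.

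A reader might infer that severe drug toxicity would quietly remove armodafinil patients. Section 5.0 limits that route: "If 1 or more armodafinil-related grade 3 or 4 toxicities is observed in the patients assigned to armodafinil, the study will be terminated". What remains is events outside that rule and withdrawal for other reasons in either arm. Removal criterion 12.18 is one possible route ("Development of symptomatic tachycardia or palpitations or uncontrolled hypertension"), though it states no grade. Section 4.22 lists palpitation at 2% and increased heart rate at 1%. Added without overlap, that is 20 × 0.03 = 0.6 expected events per arm, before asking whether they fall in the first 2 weeks.

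A reader might also infer that no analysis at all includes these patients. That goes too far, because the mixed models for secondary outcomes in section 13.22 state no 2-week cut. Nor does the promised review in section 5.0 rescue the primary analysis, since it concerns carried-forward values only.

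Finally, the gain from a mixed model is partial, and the gain figures assume a weekly schedule that the available text does not show (it refers to Appendix X). That is fair, and it is the reason for a sensitivity analysis.

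**Conclusion.** The point holds and should be fixed. The primary set is modified intent to treat, selected on a post-randomisation event, and carries the wrong label. Confidence in that is high.

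Confidence in size and direction is low. The figures above rest on an assumed number of losses, an assumed imbalance between arms and an assumed link to fatigue. A reader might infer that the estimate is biased in favour of armodafinil. The documents do not support that: the same number of losses on placebo pushes the estimate the other way, and equal or fatigue-unrelated losses leave it essentially unbiased. The strong-link results are a stress test that no section of the plan supports as likely.

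**What to change.** 1. In section 13.2, replace the two sentences under Intent to treat with: *All randomised patients are included in the primary analysis in the arm to which they were randomised.* In the regression description, change treatment received to assigned treatment.
2. Amend section 5.0 to match, so that inclusion does not depend on 2 weeks of data and carry-forward is not the primary method. Otherwise the two sections would contradict each other.
3. Use every available BFI score including baseline, for example in a longitudinal mixed model (section 13.22 already plans such models) with the AUC contrast over the primary window. First reconcile that window, which is 4 weeks in section 5.0 and 8 weeks in section 13.21.
4. Add one sensitivity analysis that imputes early dropouts unfavourably, for example predicted score plus 1 and plus 2 points for armodafinil dropouts. It is deliberately conservative.
5. Report early dropouts by arm with reasons. Section 7.17 already provides the source: "The Final Study Status Form contains data about patient disposition at the end of the study".
6. Extra patients may be randomised from added list entries (the list in section 9.0 covers 40 only), but no randomised patient is removed. If the 2-week set is also analysed, label it modified intent to treat.

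The cost is wording, a few list entries and a little more analysis, with no new data. The estimate may be slightly less favourable or less precise. Power for 0.70 SD would be about 66 to 68% instead of 70% if two early dropouts in one or both arms add almost nothing and no extra patients are randomised.
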